3.2. Secondary Objective(s)

None

4. Study Design and Endpoints**4.1. Study Design**

This randomized, double-blinded, placebo-controlled study will be conducted in two parts:

Part 1 will escalate through four sequential doses of USB002 to determine the MTD. Part 2 will determine preliminary efficacy of the USB002 MTD dose identified in Part 1.

In Part 1 (dose escalation phase), the study will follow a traditional “3+3” design with three subjects in each cohort receiving SOC plus USB002 and three subjects in each cohort receiving SOC plus placebo. Cohorts will be enrolled sequentially for USB002 dose, with subjects receiving active drug at four sequential cohort doses of 90, 300, 600 and 900 ug/kg/day. The decision to dose-escalate, de-escalate, or increase the number of subjects in any dose level will be made by a Data Safety Monitoring Board (DSMB) based on the safety review of each cohort. Escalation will continue until Part 1 enrollment is completed and the MTD is determined.

In Part 2 (dose expansion phase), subjects will be randomized 1:1 to receive either SOC plus USB002 at the MTD established in Part 1 or SOC plus placebo infusion for up to 14-days. Infusion will be discontinued at any time if $\text{SpO}_2 \geq 94\%$ on room air. Visits will continue up to Day 28, if subject is still hospitalized. The Day 28 and Day 60 follow-up visits will be conducted by phone (Telemed) if discharged.

4.2. Primary Endpoints

The primary endpoint of the study will be safety and tolerability, as demonstrated by adverse events (AE), changes in laboratory assessments, ECG assessments, vital signs, and concomitant medications (inotropes and vasopressors).

The primary endpoint of preliminary efficacy will be demonstrating the difference between USB002 and placebo groups in time to peripheral capillary oxygen saturation (SpO_2) $\geq 94\%$ on room air, sustained for at least 48 hours, through Day 28.

4.3. Secondary Endpoints

Secondary endpoints include:

- All-cause mortality at Day 60.
- Number of ventilator-free days (defined as the number of days between Visit 1/Day 1 and Day 28 that subjects are both alive and free of mechanical ventilation [MV]; freedom from MV is further defined as free from MV for at least 48 hours after extubation).
 - In the case of repeated MV, duration of MV will be summed for the purposes of calculation. In the case of tracheostomy, the same criteria apply.
- Proportion of subjects weaned from mechanical ventilation through Day 28 (defined as free from MV for at least 48 hours after extubation. In the case of tracheostomy, the same criteria will apply). This applies only to subjects on mechanical ventilation at baseline.
- Proportion of subjects progressing from non-invasive (at baseline) to mechanical ventilation. This applies only to subjects not on mechanical ventilation at baseline.
- Time to progression (TTP) from non-invasive to mechanical ventilation.
 - In the case of repeat admission to hospital and/or ICU within the first 28-days, the time from first treatment with study medication will be used to calculate TTP to MV.
- Number of days of vasoactive agent usage (defined as use of a vasoactive agent for 6 hours or more within any 24-hour period).
- Time (days) to hospital discharge.
- Changes in Ordinal Scale for Clinical Improvement (OSCI) status (see Appendix 1) from Visit 1/Day 1 to Day 28, defined as 1) time to change and 2) proportions of subjects, with 1-point and 2-point clinical status changes utilizing a time-to-event analysis from time of start of infusion (Visit 1/Day 1) of study medication to Day 28 for the time to change analysis between active and placebo groups.

4.4. Exploratory Endpoint

For any subject that is taken off assisted ventilation and study treatment is terminated earlier than planned (96 hours in Part 1 and Day 14 in Part 2), the re-initiation of assisted ventilation will be assessed as an exploratory endpoint. In the event of re-initiation of assisted ventilation, subjects who continued receiving USB002/placebo infusion will be assessed separately to those who discontinued treatment.

4.5. Study Timeline and Schedule of Events

Table 1: Schedule of Assessments (Part 1)

Assessments	Screening (72 hours)	Timepoint										Day +/- 7 days	
		Visit 1			Visit 2			Visit 3			Visit 4		
		0 hrs ²	4 hrs	8 hrs	12 hrs	24 hrs	32 hrs	40 hrs	48 hrs	72 hrs	96 hrs	End of Treatment ⁴	
Informed Consent	X												
Medical and Surgical History ¹	X												
Demographics	X												
Physical exam ³	X	X											
Chemistry	X	X											
Hematology	X	X											
Coagulation	X	X											
Urinalysis	X	X											
Pregnancy test	X	X											
12-lead ECG	X	X											
Chest X-Ray	X	X											
Vital signs	X	X	X	X	X	X	X	X	X	X	X	X	
SBT Assessment				X			X	X	X	X	X	X	
Respiratory assessments	X	X	X	X	X	X	X	X	X	X	X	X	
Blinded Dosing	X	X	X	X	X	X	X	X	X				
OSCI Status	X	X									X		X
Adverse Events		X	X	X	X	X	X	X	X	X	X	X	X
Concomitant Medication	X	X	X	X	X	X	X	X	X	X	X	X	X
Follow-Up ^{5,6} (Telemmed)												X	X

1. History to include but not limited to any significant, ongoing, or controlled with treatment, medical condition; date of hospital admission; date of ICU admission; start time of supplemental oxygen therapy; start time of nasal high-flow oxygen therapy; start time of non-invasive mechanical ventilation or mechanical ventilator via intubation.
2. If screening assessments are not completed prior to start of infusion, conduct within 24 hours of infusion start. If performed as part of screening and within 72 hours, do not repeat unless required by the Investigator. Chest X-ray and Physical Exam do not need repeating within 24 hours.
3. Physical exam to include lung auscultation.
4. Visit 5 is also End of Treatment – all End of Treatment assessments are to be conducted at Visit 5 for all subjects or for any discharge prior to Visit 5.
5. If subject is discharged from hospital, Telemed visits will be conducted once a week until Day 28, with the first occurring approximately 7 days after discharge. Day 28 and Day 60 Telemed visits will occur on Days 28 and 60, respectively, regardless of discharge date and timing of previous Telemed visits. Discharged subjects will not attend the site for visits (Days 7, 9, 12, 14, 16, 18, 21, or 24, as applicable to discharge day) or undergo procedures scheduled for those visits.
6. Telephone follow-up, if discharged. Day 28 phone call window = +/- 3 days; window not applicable if still hospitalized.

Table 2: Schedule of Assessments (Part 2)

Assessments	Timepoint (Days)										16 ⁵	18 ⁶	21 ⁶	24 ⁶	28 ^{6,7}	+/- 7 days
	Screening (72 hours)	1 ²	2	3	4	5	7	9	12	14	16 ⁵	18 ⁶	21 ⁶	24 ⁶	28 ^{6,7}	60
	End of Treatment															
Informed Consent	X															
Medical and Surgical History ¹	X															
Demographics	X															
Physical exam ³	X	X	X	X	X	X	X	X	X	X	X	X	X	X	X	
Chemistry	X	X	X	X	X	X	X	X	X	X	X	X	X	X	X	
Hematology	X	X	X	X	X	X	X	X	X	X	X	X	X	X	X	
Coagulation	X	X	X	X	X	X	X	X	X	X	X	X	X	X	X	
Urinalysis	X	X	X	X	X	X	X	X	X	X	X	X	X	X	X	
Pregnancy test	X	X	X	X	X	X	X	X	X	X	X	X	X	X	X	
12-lead ECG	X	X	X	X	X	X	X	X	X	X	X	X	X	X	X	
Chest X-ray	X	X	X	X	X	X	X	X	X	X	X	X	X	X	X	
Vital signs	X	X	X	X	X	X	X	X	X	X	X	X	X	X	X	
SBT Assessment	X	X	X	X	X	X	X	X	X	X	X	X	X	X	X	
Respiratory assessments	X	X	X	X	X	X	X	X	X	X	X	X	X	X	X	
Blinded Dosing ⁴	X	X	X	X	X	X	X	X	X	X	X	X	X	X	X	
OSCI Status	X	X	X	X	X	X	X	X	X	X	X	X	X	X	X	
Adverse Events	X	X	X	X	X	X	X	X	X	X	X	X	X	X	X	
Concomitant Medication	X	X	X	X	X	X	X	X	X	X	X	X	X	X	X	
Follow-Up ^{6,7} (Telemed)																

1. History to include but not limited to any significant, ongoing, or controlled with treatment medical condition; date of hospital admission; date of ICU admission; start time of supplemental oxygen therapy; start time of nasal high-flow oxygen therapy; start time of non-invasive mechanical ventilation or mechanical ventilator via intubation.
2. If screening assessments are not completed prior to start of infusion, conduct on Day 1, prior to infusion. If performed as part of screening and within 72 hours, do not repeat unless required by the Investigator. Chest X-ray and Physical Exam do not need repeating within 24 hours.
3. Physical exam to include lung auscultation.
4. Continuous infusion of USB002 or placebo for up to 14 days.
5. Day 16 is also End of Treatment – all End of Treatment assessments are to be conducted at Day 16 or for any discharge prior to Day 16.
6. If subject is discharged from hospital, Telemented visits will be conducted once a week until Day 28, with the first occurring approximately 7 days after discharge. Day 28 and Day 60 Telemented visits will occur on Days 28 and 60, respectively, regardless of discharge date and timing of previous Telemented visits. Discharged subjects will not attend the site for visits (Days 18, 21, or 24, as applicable to discharge day) or undergo procedures regularly scheduled for those visits.
7. Telephone follow-up, if discharged. Day 28 phone call window = +/- 3 days; window not applicable if still hospitalized.

5. Data Management

5.1. Data Management

Most data will be collected at the sites via an electronic data capture (EDC) system. The study-specific application will be developed based on the protocol requirements and following the full Systems Development Lifecycle (SDLC). The development and management of the trial application, including security and account administration, will adhere to the Standard Operating Procedures (SOPs) at McDougall Scientific (a division of Alimentiv Inc.), in Toronto, Canada, the CRO retained by US Biotest to perform the statistics and data management functions for the trial.. All participants will be trained in the use of the application, and the training documented prior to each site being initiated.

The application design will, where appropriate, provide choice fields in the form of checkboxes, buttons and lists to aid in ensuring high quality standardized data collection. In addition Data Logic Checks (or data Edit Checks) will be built into the application based on variable attributes (e.g. value ranges), system logic (e.g. sequential visit dates) and variable logic (e.g. onset date must be before cessation date). Visual review and data responses will be overseen by a trained data manager.

The database will be locked when all the expected data has been entered into the application, all query responses have been received and validated, the designated data has been noted as monitored in the system and each investigator has signed off the casebook for each of their study subjects. The data coding must be accepted by the Sponsor and any Serious Adverse Events (SAEs) reconciled with the pharmacovigilance data base working with the Medical Monitor.

The data management processes are outlined in the project specific Data Management Plan (DMP); this and all related documentation are on file at McDougall Scientific and are identified by the project code US21TXK.

5.2. Coding

The medical history and adverse events were coded in MedDRA version 24 and signed off by US Biotest. All concomitant medication was coded using WHO Drug (version 2021 March) and reviewed and signed off prior to data base lock.

5.3. Missing Data

All missing data from CRF will not be imputed. Missing data will be considered missing at random.

5.4. Data Conversion for Analysis

To summarize quantitative endpoints, e.g., lab test results, some data collected as text values need to be converted to numeric values for analysis. Following conventional rules will be applied for this study.

- All "< xx" lab results will be converted to $0.99 * xx$. The adjustment is -1% of xx.

All "> xx" lab results will be converted to $1.01 * xx$. The adjustment is +1% of xx.

Above data conversions are only applied to data descriptive summaries. In by-subject data listings, original reported data "< xx" or "> xx" will be presented.

For this study's data submission and analysis, all EDC and external data will be converted to SDTM (Study Data Tabulation Model) and ADaM (Analysis Data Model) datasets. In the creation of SDTM and ADaM datasets, original lab test results from different sites (laboratories) need to be converted to results in SI units (the International System of Units). For some tests, data rounding may be applied during the conversion. The details will be provided in SDTM and ADaM's define.xml files and their support documents.

6. Change to Analysis as Outlined in the Protocol

6.1. Analysis of Part 2 Data

Due to the early termination of the study, no Part 2 (dose expansion phase) subject is enrolled. All analyses for Study Part 2 (dose expansion phase) will not be performed.

6.2. Time to Achieving 1-point and 2-point OSCI Score Decreases

According to the Protocol, time from Study Day 1 to achieving 1-point and 2-point OSCI decreases will be analyzed using time-to-event method.

Due to the early termination of the study and the small number of subjects in each treatment group, the outcomes will only be summarized descriptively. No time-to-event (Kaplan-Meier) estimates or curves will be provided. See section 8.3.8 for details.

6.3. Using of Vasoactive Agent

Protocol describes two efficacy endpoints about the using of vasoactive agent:

- The requirements for inotropes and vasopressors
- Total days of using vasoactive agent

These data are not captured by eCRF in separate eCRF form(s). Because of the early termination of the study, Sponsor decides that these endpoints will not be analyzed.

7. Statistical Methods

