3.1. Primary Objective

The primary objectives of safety and tolerability of USB002 will be evaluated for rate of occurrence and severity of AEs resulting from clinical changes (Visit 1/Day 1 to Day 28): cardiovascular parameters, to include blood pressure (BP), heart rate (HR), 12-lead electrocardiogram (ECG), and requirements for inotropes and vasopressors; laboratory parameters, to include kidney and liver function.

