8.2. Primary Outcomes

The primary endpoint of the study will be safety and tolerability, as demonstrated by adverse events (AE), changes in laboratory assessments, ECG assessments, vital signs, and concomitant medications (inotropes and vasopressors). These outcomes will be summarized by cohort. See details in sections 8.2.1 to 8.2.6.

Co-primary endpoint is the difference between USB002 and placebo groups in time to peripheral capillary oxygen saturation (SpO₂) $\geq 94\%$ on room air, sustained for at least 48 hours, through Day 28. All peripheral capillary oxygen saturation (SpO₂) results from baseline to Day 28 will be listed (and summarized if applicable). See section 8.2.7.

No statistical inference will be made for primary endpoint.

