8.2.6. Time to peripheral capillary oxygen saturation (SpO_2) $\geq 94\%$ on room air

The time from baseline to achieving $\text{SpO}_2 \geq 94\%$ on room air will be calculated for each subject. Two summaries will be provided:

- All subjects treated with USB002 vs. all placebo subjects
- USB002 subjects vs. placebo subjects by cohort. That is, comparing between two treatment groups within each cohort (dose level)

All data will be listed.

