8.3.6. Time to hospital discharge

Total days from Day 1 to hospital discharge will be listed and summarized.

8.3.7. Change of OSCI status from Day 1 to Day 28

For each subject, following outcomes will be calculated:

- Days from baseline to the date with OSCI score decreased 1-point from baseline
- Days from baseline to the date with OSCI score decreased 2-point from baseline
- OSCI score change from baseline to Day 28
- Achieving 1-point decrease of OSCI score at Day 28 (Yes/No)
- Achieving 2-point decrease of OSCI score at Day 28 (Yes/No)

These outcomes will be summarized.

All OSCI data will be listed.

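### SAP 6.3 drops the requirement for inotropes and vasopressors as an efficacy endpoint, but it is a primary safety outcome that SAP 8.2 still promises to summarise by cohort

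*SAP*

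**What the plan says.** SAP 6.3 opens with "Protocol describes two efficacy endpoints about the using of vasoactive agent" and lists two items: the requirement for inotropes and vasopressors, and the total days of vasoactive use. It notes that no separate eCRF form collects these data and concludes: "Because of the early termination of the study, Sponsor decides that these endpoints will not be analyzed".

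Elsewhere the first item is a safety outcome. SAP 3.1 puts it in the primary safety and tolerability objective: "and requirements for inotropes and vasopressors; laboratory parameters, to include kidney and liver function". SAP 4.2 names inotropes and vasopressors in the primary safety endpoint. SAP 8.2 repeats this and commits to a table: "vital signs, and concomitant medications (inotropes and vasopressors). These outcomes will be summarized by cohort. See details in sections 8.2.1 to 8.2.6". The protocol agrees on the classification: the synopsis lists the item under safety, and section 2.1.1 includes it in the primary safety objective. Of the two items in SAP 6.3, only days of use is an efficacy endpoint in the protocol (section 2.1.2, secondary).

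**The concern.** A programmer cannot follow both SAP 6.3 and SAP 8.2. If 6.3 is followed, a component of the primary safety outcome disappears, and the record of changes describes it as the loss of an efficacy endpoint. A reader of the study report would not learn from section 6 that the primary safety outcome had been reduced.

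The item is not marginal for this drug. Protocol 3.2 names hypotension (systolic BP below 90 mmHg), possibly needing fluids or IV pressors, as a possible DLT. Protocol 5.5 asks for post-infusion vasopressors to be captured because USB002 may affect blood pressure. New pressor use by dose is therefore a direct measure of tolerability in a dose-escalation study.

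**Working it through.** There is no planned figure to reproduce. The check compares the sections and then sizes what is lost.

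**1. Where the promised summary should be.** SAP 8.2 points to 8.2.1 to 8.2.6. Those subsections cover adverse events, respiratory results, laboratory tests, ECG, vital signs and time to SpO2. None covers inotropes or vasopressors, and the derivation table in SAP 7.2 has no entry for them.

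**2. Cross-references.**
- SAP 8.2 sends the SpO2 outcome to a section that does not exist ("will be listed (and summarized if applicable). See section 8.2.7"). It is at "8.2.6. Time to peripheral capillary oxygen saturation".
- SAP 6.2 says "See section 8.3.8 for details" for the OSCI outcome. It is at "8.3.7. Change of OSCI status from Day 1 to Day 28".
- SAP 4.3 lists 8 secondary endpoints and SAP 8.3 has 7 subsections. The missing one is days of vasoactive use, sixth in the list.

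Both references are one too high. That is what would be left if one subsection had been removed from each of 8.2 and 8.3 without renumbering the references. The wrong references are facts; the explanation is an inference.

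**3. Do the stated reasons prevent the analysis?**
- *No separate form.* Protocol 5.5 and SAP 8.4.1 require concomitant medications in the eCRF and name post-infusion vasopressors specifically. Protocol 7.2.1.3 lists medications with start and stop dates. Protocol 4.2 excludes patients on vasopressors when the infusion starts, so a vasopressor begun afterwards is new use. A yes/no outcome can be derived from this.
- *Early termination.* Adverse events, laboratory tests, ECG and vital signs are still summarised in the same subjects.

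**4. What the remaining tables show.** SAP 8.4.1 gives tables by ATC level 2 and level 4, before and after first infusion. Read with SAP 8.1, these may be split by dose. They count users per row, and one subject can appear in several rows. The TEAE tables in 8.2.1 classify events by severity, relationship and outcome, not by whether a pressor was given.

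**5. Size.** SAP section 2 gives 6 + 6 + 6 + 3 = 21 enrolled subjects.
- By design each completed dose has 3 active subjects. One subject is 1/3 = 33.3%, with exact (Clopper-Pearson) 95% CI 0.8% to 90.6%. Two subjects are 2/3 = 66.7%, CI 9.4% to 99.2%.
- Completed cohorts give 3 × 3 = 9 placebo subjects. The split of Cohort 4's 3 subjects is not stated, so pooled placebo is 9 to 12. One placebo subject is 1/12 = 8.3% to 1/9 = 11.1%.
- If two ATC rows show a and b users out of n, the number with any use lies between max(a, b) and min(a + b, n). With assumed counts a = b = 1 and n = 3, that is 1 to 2 subjects: 33% or 67% of the dose group. The ATC table cannot tell these apart.

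**The case against.** The removal is declared openly, in the SAP section for changes from the protocol. Only SAP 8.2 asks for a by-cohort summary. Protocol 2.1.1 and SAP 3.1 frame the objective as adverse events resulting from clinical changes, with pressor requirements among the parameters, and Protocol 7.2.3 has no pressor subsection. A once-per-subject table is therefore one choice of format, and the contradiction could also be settled by justifying the removal and editing 3.1, 4.2 and 8.2. SAP 8.1 says all EDC data will at least be listed, so with 21 subjects a reader could work out who received what. No inference is planned, the interval for 1/3 is very wide, and escalation decisions rest with the DSMB. The numbering errors are weak evidence of incomplete removal, because SAP 8.1 also misdirects efficacy outcomes to 8.2.1 and 8.2.2.

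Much of this stands as qualification. The by-cohort instruction comes from the SAP alone, the information is obscured rather than wholly lost, and the cause of the wrong references is unproven. It does not remove the problem. The change is declared under the wrong label, so the loss of a primary safety component is not disclosed as such. A listing is not a summary of a primary outcome. Small numbers have not stopped the other primary safety outcomes from being tabulated. A justified removal would make the SAP consistent, but the reasons now given do not justify one.

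**Conclusion.** The concern holds. SAP 6.3 misclassifies a primary safety component and cancels a summary that SAP 8.2 promises. Following 6.3, no planned table gives the number of subjects at each dose who newly needed any inotrope or vasopressor. With 3 active subjects per completed dose, misreading one subject moves the figure by 33 percentage points. The data would be descriptive and imprecise at best, so this should be fixed for the integrity of the primary safety reporting; it does not affect any inference.

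This assumes that the three completed cohorts were split 3 and 3 as designed, that all 21 enrolled subjects were treated, and that post-infusion vasopressors were recorded as Protocol 5.5 requires. The documents do not show whether hours of use were recorded. If they were not, dropping the days-of-use endpoint is defensible.

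**What to change.** 1. In SAP 6.3, relabel the requirement for inotropes and vasopressors as a primary safety outcome. Limit the exclusion to the days-of-use endpoint (6 hours or more in any 24 hours), and only if hours of use were not recorded.
2. Add an 8.2 subsection and a 7.2 derivation: the number and percentage of FAS subjects who start any inotrope or vasopressor after the start of first infusion, each subject counted once, by dose level and pooled placebo, with study day of first use. Derive it from the coded concomitant medications and their start dates. The exclusion criterion names vasopressors only, so use start dates rather than assume that no inotrope was running at baseline. Fix the list of coded terms before unblinding.
3. Correct the references to 8.2.7 and 8.3.8, and the pointer in 8.1 that sends efficacy outcomes to 8.2.1 and 8.2.2.

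If the sponsor still wishes to drop the item, 3.1, 4.2 and 8.2 must be changed to match, and 6.3 must justify it as a change to the primary safety outcome.

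Optional, not an error correction: in 8.2.5, summarise the lowest post-infusion systolic BP and the number of subjects with any reading below 90 mmHg (the protocol's own figure), summarise the lowest triggered mean arterial pressure separately, and restore the flagging of notable values in the listings that Protocol 7.2.3.3 describes.

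The cost of items 1 to 3 is one extra table from data already required in the EDC, a short review of coded terms, and text corrections in 6.2, 6.3, 7.2, 8.1 and 8.2.
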